5.2.3 Inclusion criteria for continued access registry

Candidates for the continued access registry must meet all of the following inclusion criteria:

- (1) Patients determined by the heart team to be unable to undergo safe open surgical therapy, and judged EWJ-003 is the best available treatment. Specifically, considering the followings as risk factors, the risk should be comprehensively determined.
- Porcelain aorta
 - History of mediastinal radiotherapy
 - History of mediastinitis
 - Remarkable thoracic deformity
 - Previous open heart surgery or coronary-artery bypass grafting
 - Chronic obstructive pulmonary disease
- (2) Patient has senile degenerative AS with one of the following echocardiographic criteria. Measurement of AVA at baseline must be acquired within 60 days prior to the study procedure.
- a. Mean pressure gradient ≥ 40 mmHg
 - b. Aortic flow velocity ≥ 4.0 m/s
 - c. AVA at baseline ≤ 1.0 cm²
 - d. AVA index ≤ 0.6 cm²/m²
- (3) Patient has symptoms associated with AS \geq NYHA class II.
- (4) The subject has been informed of the nature of the study, agrees to its provisions and has provided written informed consent as approved by the IRB of the respective clinical sites.
- (5) The subject and the investigator agreed to comply with all required post-procedural follow-up visits.
- (6) Patient on maintenance dialysis (hemodialysis or peritoneal dialysis).
- (7) Patient has any one of the following native aortic valve annulus sizes as measured by TEE or 3D-CT.
- a. Native annulus size ≥ 16 mm and ≤ 28 mm by TEE
 - b. Native annulus area ≥ 273 mm² and ≤ 683 mm² by 3D-CT
 - c. Area-derived diameter ≥ 18.6 mm and ≤ 29.5 mm by 3D-CT

<Rationales for the setting>

For patients deemed possible for safe treatment with EWJ-003, but do not meet all of the inclusion criteria described in Section 5.2.1, and therefore no chance of treatment, to make it possible to receive treatment with EWJ-003 on humanitarian grounds, for the continued access registry, the following changes were made to the inclusion criteria described in Section 5.2.1.

Table 5-1: Changes made to inclusion criteria

Inclusion criteria described in Section 5.2.1	Inclusion criteria for continued access registry	Reason for change
(6) Patient has been on dialysis (hemodialysis or peritoneal dialysis) in stable condition for ≥ 3 months.	(6) Patient on maintenance dialysis (hemodialysis or peritoneal dialysis).	Based on the Guidelines for Clinical Evaluation of Therapeutic Drugs for Renal Anemia ^[46] unstable patients at early stage of dialysis were excluded for appropriate evaluation of the safety and efficacy of EWJ-003. However, the continued access registry is not aiming at evaluation of the efficacy and safety of EWJ-003, and therefore not limiting a history of dialysis, and whether or not the patient can be treated with EWJ-003 can be determined taking individual patient's condition and safety into consideration, this change was made.
(8) Patient is verified by the Case Review Process that the treatment with EWJ-003 is appropriate for the patient.	(Deleted)	Because in the continued access registry case review is not mandatory, this criterion was deleted.

5.2.4 Exclusion criteria for continued access registry

Candidates for the continued access must not fall under any one of the following exclusion criteria:

- (1) Patient has an evidence of an acute MI within 1 month (30 days) prior to the study procedure. Acute MI is defined as; Q wave MI, or non-Q-wave MI with elevation of CK-MB or troponin, together with the evidence of myocardial ischemia with at least one of the following findings:
- Symptoms of ischemia
 - ECG changes indicative of new ischemia (ST-T changes, LBBB)
 - Imaging evidence of a new loss of viable myocardium or new wall motion abnormality.
- (2) Patient has a congenital unicuspid or bicuspid. Or patient has a non-calcified aortic valve.
- (3) Patient has severe aortic valve incompetence.
- (4) Patient has severe mitral valve incompetence.
- (5) Patient has an evidence of any therapeutic invasive cardiac procedures within 30 days prior to the study procedure. However, implantation of a permanent pacemaker or balloon valvuloplasty for bridging to procedure after a qualifying echocardiography are excluded.
- (6) Patient with planned concomitant surgical or transcatheter ablation for atrial fibrillation.
- (7) Patient has pre-existing prosthetic valve in any position.

- (8) Patient is at a high risk of bleeding, difficult to have appropriate treatment, or unable to receive appropriate anticoagulation or antiplatelet therapy.
- Leukopenia (white blood cell $< 3,000$ cells/mm³)
 - Thrombocytopenia (platelet $< 50,000$ cells/mm³)
 - Bleeding diathesis or coagulopathy
 - Active gastro-intestinal ulceration, or upper gastro-intestinal bleeding within the past 3 months
 - Refuse blood transfusion
 - Receiving anticoagulant and/or antiplatelet medication and can't stop them for the study procedure
 - Concluded by investigator that appropriate anticoagulation or antiplatelet therapy is difficult for any other reasons
- (9) Patient has untreated clinically significant coronary artery disease requiring revascularization.
- (10) Patient has hemodynamic instability requiring mechanical heart assistance. Patient has respiratory instability requiring mechanical ventilation.
- (11) Patient requires an emergency surgery for any reason.
- (12) Patient has hypertrophic cardiomyopathy with or without obstruction.
- (13) Patient has severe ventricular dysfunction with LVEF $< 20\%$.
- (14) Patient has echocardiographic evidence of intracardiac mass, thrombus, or vegetation.
- (15) Patient has hypersensitivity to or a known contraindication of heparin and/or aspirin, which cannot be adequately pre-medicated. Patient has a known hypersensitivity to contrast media.
- (16) Patient has hypersensitivities to cobalt, chromium, nickel, molybdenum, titanium, manganese, silicon, or polymeric materials.
- (17) Patient has had a cerebrovascular accident or transient ischemic attack within 6 months prior to the study procedure. Except cases with an event associated with AS.
- (18) Patient with poorly controlled blood pressure.
- (19) Patient has serum albumin < 2.8 g/dL or BMI < 16 .
- (20) Patient has uncontrollable diabetes mellitus.
- (21) Patient has active bacterial endocarditis or other active infection.
- (22) Patient has life expectancy < 12 months due to pre-operative non-cardiac comorbidity (e.g., cancer, chronic liver disease).
- (23) Currently participating in an investigational drug or another device study. [Note: Trials requiring extended follow-up for products that were investigational, but have since become commercially available, are not considered investigational trials.]
- (24) Cardiovascular surgeons and cardiologists concluded that the patient is inappropriate for participating in this trial.

<TF approach>

- (25) Patient has significant tortuous aorta, diseases including abdominal aortic or thoracic aneurysm, or significant atheroma in the femoral artery or iliac artery that would prevent from proper placement of delivery system.
- (26) Patient has iliofemoral vessel characteristics that would preclude safe placement of 14F or 16F introducer sheath such as severe obstructive calcification and severe tortuosity, or minimum average vessel size less than 5.5 mm (6.0 mm for 16F introducer sheath).

<Rationales for the setting>

For patients deemed possible for safe treatment with EWJ-003, but fall under one of the exclusion criteria described in Section 5.2.2, and therefore no chance of treatment, to make it possible to receive treatment with EWJ-003 on humanitarian grounds, for the continued access registry, the following changes were made to the exclusion criteria described in Section 5.2.2.

Table 5-2: Changes made to exclusion criteria

Exclusion criteria described in Section 5.2.2	Exclusion criteria for continued access registry	Reason for change
(10) Patient has hemodynamic instability requiring inotropic agents or mechanical heart assistance. Patient has respiratory instability requiring mechanical ventilation.	(10) Patient has hemodynamic instability requiring mechanical heart assistance. Patient has respiratory instability requiring mechanical ventilation.	Some patients need prophylactic inotropic agents before and during dialysis for smooth dialysis although the hemodynamics does not interfere with safe implantation of EWJ-003, and therefore irrespective of with or without inotropic agents, whether or not the patient can be treated with EWJ-003 can be determined taking individual patient's condition and safety into consideration, this change was made.
(19) Patient has serum albumin < 3.0 g/dL or BMI < 18.	(19) Patient has serum albumin < 2.8 g/dL or BMI < 16.	For the continued access registry, the exclusion criteria were set up, based on the serum albumin 2.8 g/dL, the physiological reference value that induces edema associated with decreased visceral protein mass due to malnutrition, ^[32] and BMI 16, the reference value that causes a significantly higher mortality risk in Japanese older adults. ^[33]

[figure not shown]
5.3 Case Review Process

The results of screening conducted by the heart team in the study site confirmed that all of the inclusion criteria were satisfied, and none of the exclusion criteria were met, and patients who were deemed eligible for this clinical trial will be eventually determined for their eligibility by the case review. The case review should be conducted by at least one investigator and/or subinvestigator from a study site other than the screening site, and when eligibility of the patient is approved, the patient can be registered as a subject in this clinical trial. For detailed case review procedure, see the "Japan Case Review Procedure."

Case review is not mandatory in the continued access registry. When the results of screening conducted by the heart team in the study site confirmed that all of the inclusion criteria were satisfied, and none of the exclusion criteria were met, the patient is regarded as eligible for this clinical trial. When a case review is performed as necessary, it should be based on the same procedure as that of the main clinical trial.

5.4 Subject Enrollment

For patients who were eventually determined to be eligible for this clinical trial by case review, enrollment in this clinical trial should be completed by the document describing the patient's eligibility. For the continued access registry, patients deemed eligible for this registry by screening will be enrolled in this registry by the start of study procedure (at the time point when an invasion such as an incision is made on the access site). For the subject selection/enrollment flow, see Figure 5-1.

Note: Case review is not mandatory in the continued access registry. Patients deemed eligible for the continued access registry by screening conducted by the heart team of the study site will be regarded as registered in this registry by the start of study procedure (at the time point when an invasion such as an incision is made on the access site). Even after case review, the patient will be regarded as completed registration in this registry by the start of study procedure.

6 CONSIDERATIONS CONCERNING SUBJECT'S INFORMED CONSENT

Subject's informed consent should be obtained in compliance with the followings:

- (1) The principal investigator or subinvestigators will give an explanation about this clinical trial to subjects, using written patient information approved by the IRB and other appropriate documents, and obtain written informed consent to participation in this clinical trial voluntarily signed by the subjects.
- (2) Before informed consent may be obtained, the principal investigator or subinvestigators should provide the subject with ample time and opportunity to inquire about details of the trial and to decide whether or not to participate in the trial. The subject should fully understand the contents of the clinical trial, and then sign or place name and a seal and date the informed consent form that describes consent to participation in this clinical trial. The principal investigator or subinvestigators who provided an explanation to the subject should sign or place name and a seal and date the informed consent form. However, if a subject is unable to read the written patient information due to physical problem and so on, but can understand the contents of the written patient information given orally or other communication means, an impartial witness should be present during the informed consent discussion. In such a case, in addition to the subject, the witness should sign or place name and a seal and date the informed consent form. When a study staff provided a supplemental explanation, also the study staff should sign or place name and a seal and date the informed consent form.
- (3) The principal investigator, subinvestigators, or study staff (hereinafter referred to as "investigators") should enter the date of subject's written informed consent, and if a witness is required, the date of witness, in the electronic case report form (eCRF).
- (4) The principal investigator or subinvestigators must not perform tests for the purpose of this clinical trial until after acquisition of written informed consent. The principal investigator or subinvestigators should confirm whether or not the subject has other personal physician, and after an agreement with the subject, inform the personal physician of the subject's participation in this clinical trial. If the subject may be newly consulting other hospital/department after participation in this clinical trial, the principal investigator or subinvestigators should instruct the subject to inform the new hospital/department of participation in this clinical trial.
- (5) If information becomes available that may be relevant to the subject's willingness to continue participation in the trial, the principal investigator or subinvestigators should inform the subject in a timely manner, confirm as to whether or not the subject is willing to continue the trial, and record it in the medical records, etc.
- (6) If the principal investigator considers that the written patient information should be revised, the

written patient information should be revised promptly based on the relevant information. The principal investigator should notify the director of the study site of the revised written patient information, and obtaining IRB's approval. After approval, the principal investigator or subinvestigators should obtain the subject's voluntarily signed written consent to continued participation in this clinical trial. If a witness is required, follow (2).

- (7) The investigators should enter the date of subject's written informed consent, and if a witness is required, the date of witness, in the eCRF. Further, if legally acceptable representative is required, the investigators should enter the date of consent given by the legal representative in the eCRF.
- (8) The principal investigator or subinvestigators will provide the subject with a copy of signed or name and seal placed informed consent form and written information. The original informed consent form signed or name and a seal placed should be retained by the study site.

7 TREATMENT OF SUBJECTS

7.1 Baseline Tests

The subjects enrolled in this clinical trial will receive tests to obtain baseline values before the procedure, so as to confirm the impact of the THV on patients, compared with follow-up observation values after the procedure. These test results will be entered in eCRFs and will be used for determination of eligibility of the subjects. If there are some data of tests carried out within the permissible time range of baseline tests available, even the results of tests carried out before acquisition of informed consent or to confirm subject's eligibility may be used as baseline data.

For baseline test/observation items and timing, see Sections 10.1 and 10.2.1.

7.2 Study Procedure

In this clinical trial, the investigational valve may be implanted by either TF, TA, or TAO approach. However, TF approach should be the first line of treatment, and when TF approach is difficult to perform, carefully examine the subject's clinical and anatomical characteristics, and then select appropriate access site (TA or TAO approach).

For deployment of the THV, the balloon should be inflated at a nominal volume (see Section 3.2 Table 3-2), and if dilatation at a nominal volume is impossible for medical reasons, the subject should be included in the bailout treatment registry (see Section 7.4 "Bailout Treatment Registry"). In the continued access registry, irrespective of whether the THV was implanted at a nominal volume or not, subjects who received the study procedure will be included in this registry. For preparation of study device, THV rinsing, and detailed implantation procedure, see Attachment 2 "Instructions for Use." In order to ensure and protect the

- 64 -

safety of the subjects, the sponsor should witness all procedures as much as possible and consider to be able to respond to questions about the study device and study procedure.

If severe aortic valve regurgitation is observed after implantation of the THV, a valve-in-valve procedure may be performed. When a valve-in-valve procedure is required, as a general rule, the study device should be used. Since sufficient evidence has not been obtained for the safety and efficacy of the valve-in-valve procedures, a physician who performs implantation should carefully select the size and perform the implantation procedure.

7.3 Post-procedural Follow-up Observation

All subjects for whom the THV was implanted and maintained at the time point when the subject left the operation room should undergo the 5-year post-procedural follow-up observation specified in the protocol. For study discontinuation subjects without implantation of the investigational valve for the reasons that the procedure was switched to surgery, or already approved TAVI bioprosthetic valve was implanted, participation in this trial should be discontinued at the time point, and follow-up observation will not be required thereafter.

For the test/observation items and timing in the post-procedural follow-up observation, see Section 10.

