10.2.9 At trial discontinuation

At trial discontinuation, collect the data on the following items. If any AE is found at discontinuation, a follow-up investigation should be performed, and also the safety after discontinuation should be followed up as much as possible. For detailed subject’s trial discontinuation, see Sections 14.1 and 14.2.

- Anticoagulant/antiplatelet drugs
- Other concomitant drugs/therapies (until 1 year post-procedure)
- AE/device deficiency
 - For a patient who has suffered a stroke within 1 year post-procedure, mRS must be evaluated within 30 to 90 days and beyond 90 days as earlier as from the onset of stroke.

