11.7 Follow-up Investigation of Adverse Events

The investigators must follow up AEs until recovery as a general result or disease condition is stabilized, except for the following cases, and must report the additional information on the disease condition resulted from the follow-up investigation to the sponsor.

- The principal investigator or subinvestigators judges that the outcome of the AE cannot be recorded because the AE is permanent with no prospect of recovery, etc.
- The AE is exacerbation of pre-existing complication.
- The subject is lost to follow-up.

- 99 -

- The principal investigator or subinvestigators judges that a follow-up investigation until recovery is unnecessary.

AEs sustained at the end of the clinical trial or discontinuation of the trial, except for the above-mentioned cases, should be followed up until recovery or the disease condition is stabilized.

The study sites must submit source documents required for event adjudication by CEC of all death cases and cases with stroke occurred up to 1 year post-procedure via the monitor as much as possible. The source documents required for event adjudication are as shown in Table 13-1, but not limited to those. When provision of additional information is requested by the CEC, the study sites should respond as much as possible.

Table 13-1: Source documents required for event adjudication by CEC

Time of death	Time of stroke onset

 Death certificate Autopsy record¹ Discharge record 	
 Head neuroimaging (head CT/MRI)² Medical record Medical record by a neurologist/neurosurgeon mRS

¹When available

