14 SUBJECT TREATMENT DISCONTINUATION

14.1 Subject Treatment Discontinuation

Enrolled subjects will continuously participate in the clinical trial until all follow-up observations specified in the protocol are completed. However, the following subjects should discontinue the trial.

- A subject or the legal representative requests discontinuation of the participation in the clinical trial.
- The principal investigator or subinvestigators judges that continued trial will be a disadvantage for subject's health condition.
- The study procedure has not been started.
- When the subject is exiting the operation room, the investigational valve has not been implanted.
- The investigational valve was removed.
- The subject died.
- Continued participation in the clinical trial was deemed difficult.
- The sponsor requests (continued trial was determined to be a disadvantage in the subjects).

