14.2 Subject Treatment Discontinuation Procedure

When a subject discontinues participation in the clinical trial, the following procedure should be used.

- The investigators should enter the date of discontinuation, reason for discontinuation, AE incidence status, and drug therapy status in the eCRFs. To ensure the safety of discontinued subjects, all possible measures should be taken, appropriate treatment should be given, and also for the safety after discontinuation, perform follow-up investigation as much as possible.
- If a subject discontinued the trial due to a safety issue arise from an incidence of AE or worsened disease, the investigators enter it in the eCRF in accordance with Section 11 "ADVERSE EVENTS."
- If an AE is found at the time of discontinuation, the investigators should perform a follow-up investigation of the AE.
- The investigators should promptly inform the sponsor of the subject's treatment discontinuation.

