14.3 Follow-up Investigation of Subjects with Missing Visits

If a subject miss the follow-up observation as specified in the protocol because the subject failed to visit, the investigators should contact the subject as much as possible to investigate the subject's health condition (confirmation of survival, the presence or absence of an AE). In such a case, enter the contact means, date of contact, subject's condition, and the reason for missing visit in the eCRF. When after trying to contact to the subject, but the subject could not be reached, enter the fact, date of contact, contact means the eCRF.

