15.1.1.2 As-treated analysis set

A subject population consisting of subjects who were enrolled in this clinical trial and implantation of the study device was initiated is defined as as-treated (AT) analysis set. The time when invasion such as incision was made on the access site is regarded as the start of the study procedure. The primary endpoint and secondary safety and efficacy endpoints will be analyzed in the AT analysis set.

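### Follow-up may end before day 365 for some subjects in the primary as-treated set, and nothing requires their 1-year vital status

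*Combined protocol and SAP*

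**What the plan says.** Section 15.1.1.2 defines the AT set as enrolled subjects in whom implantation was initiated, and places the start of the procedure at the access-site incision. It then states: "The primary endpoint and secondary safety and efficacy endpoints will be analyzed in the AT analysis set". Only the valve implant set (15.1.1.3) removes subjects switched to surgery or given a different transcatheter valve.

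For subjects who leave without the study valve for either of those reasons, Section 7.3 says "participation in this trial should be discontinued at the time point, and follow-up observation will not be required thereafter". Section 14.1 lists further grounds for discontinuation, among them "The investigational valve was removed" and the case where the investigator "judges that continued trial will be a disadvantage for subject's health condition".

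What the protocol asks for after discontinuation is limited:

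- Section 10.2.9: "also the safety after discontinuation should be followed up as much as possible".
- Section 14.2: "perform follow-up investigation as much as possible".
- Section 11.7: adverse events still present at discontinuation "should be followed up until recovery or the disease condition is stabilized", with listed exceptions.
- Section 14.3 does name "confirmation of survival, the presence or absence of an AE", but for subjects who fail to attend a protocol visit.
- The glossary (Section 30) closes adverse event capture at discontinuation.

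Section 15.1.2 specifies a one-sided exact test against the 45% performance goal, makes Kaplan-Meier estimation optional, and leaves detail to a separate Statistical Analysis Plan that is not among the documents reviewed.

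**The concern.** The set in which the primary endpoint is tested and the set that must be followed to the endpoint are not the same. A subject converted to surgery after incision counts in the AT denominator, yet the protocol lets follow-up stop that day. A subject explanted at month 3 is in the same position from month 3.

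The loss is unlikely to be random. The glossary defines a switch to surgery as the result of a procedure-related complication, and these patients were enrolled because safe open surgery was judged not possible. A death from the complication itself would usually be caught through Section 11.7. The exposed deaths are those that occur after the event has stabilised and before day 365.

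Unrecorded deaths push observed mortality down, towards success. With about 30 subjects, and no replacement of discontinued ones (Section 4.3), the result can turn on a single death.

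**Working it through.** **Inputs.** Null mortality 45%, assumed mortality 20%, one-sided alpha 0.05, 24 evaluable and 30 enrolled subjects (Section 4.3). Upper mortality figure 26.9% (Section 4.3, rationale for the predicted mortality). Conversions to surgery: 1 of 583 in the US trial and 1 of 102 in the EU trial (Section 1.2.2.1). All probabilities are exact binomial.

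**Reproducing the plan's figure.** At n = 24 the largest count c with P(X ≤ c | 24, 0.45) ≤ 0.05 is 6 (exact alpha 0.0364). Power = P(X ≤ 6 | 24, 0.20) = 0.811, which is the stated 81.1%.

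**Margin at n = 30.** The cutoff is 8 deaths, with exact alpha 0.0312 and power 0.871.

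- 8/30: p = 0.031, success.
- 9/30: p = 0.069, failure.
- 8/29 (one of nine deaths lost and the subject dropped): p = 0.043, success.

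The probability of landing on exactly 9/30 is 6.8% at 20% mortality, 14.6% at 26.9% and 3.8% at 45%. At every AT size from 24 to 30, one missed death counted as alive turns the nearest failing result into a success. Dropping the subject does so at 25, 27, 28 and 30, but not at 24, 26 or 29.

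**The handling rule alone can decide.** Take 8 observed deaths and 2 unknowns. Counted alive, 8/30 succeeds (p = 0.031). Excluded, 8/28 fails (p = 0.058). Counted as deaths, 10/30 fails.

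**Expected bias from conversions.** P(at least one in 30) = 1 − (1 − r)^30, which is 5.0% for r = 1/583 and 25.6% for r = 1/102. Suppose a fraction m of converted subjects die, every such death is missed and counted alive, and true overall mortality is 45%. Type I error is then P(X ≤ 8 | 30, 0.45 − r·m):

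| r | m = 0.6 | m = 0.7 | m = 1.0 |
|---|---|---|---|
| 1/583 | 0.0320 | 0.0321 | 0.0325 |
| 1/102 | 0.0360 | 0.0368 | 0.0395 |

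The reference value is 0.0312, so all six stay below 0.05.

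**Stress test.** Fix k unfollowed subjects and assume 60–70% of them die; no document gives this figure. With overall mortality held at 45%, mortality in the followed is q = (30 × 0.45 − k·m)/(30 − k). For k = 2 and m = 0.7, q = (13.5 − 1.4)/28 = 0.432. Type I error is P(X ≤ 8 | 30 − k, q) if they are counted alive, or uses the cutoff for 30 − k subjects if they are dropped (8, 7 and 7 for k = 1, 2 and 3):

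| k | counted alive | dropped |
|---|---|---|
| 1 | 4.8–5.2% | 4.8–5.2% |
| 2 | 7.2–8.3% | 3.1–3.7% |
| 3 | 10.6–12.8% | 4.9–6.2% |

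If exactly one death were always missed and counted alive, type I error is P(X ≤ 9 | 30, 0.45) = 6.9%.

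**The case against.** The best case on the other side has five parts.

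1. **Who is in the set.** Section 15.1 says evaluation is in subjects whose valve was dilated at nominal volume. Read literally, that leaves out a subject converted before deployment. However, that paragraph serves to separate the bailout and continued access subjects, and the explicit AT definition and its assignment to the primary endpoint prevail. Explanted and investigator-discontinued subjects are affected on either reading. The conflict is real and should be reconciled.
2. **Size.** At documented conversion rates the error stays below 5%. At those rates the chance of two or more conversions in 30 is only 0.1–3.5%, so the k = 2 and k = 3 rows are unlikely to arise from conversions alone. This stands. The rates come from trials that excluded chronic dialysis patients, though, and say nothing about explants, use of another valve or investigator-decided discontinuation, for which no rate is given.
3. **Existing follow-up.** Sections 10.2.9, 11.7 and 14.2 are not silent. But they are best-effort or limited to an ongoing event, name no time point and do not name vital status.
4. **The separate Statistical Analysis Plan** may contain a rule for unknown status. It may, but an analysis rule does not create a duty to collect the data.
5. **Timing.** Enrolment into the analysis population is marked closed. For that cohort the remedy may amount to retrospective ascertainment, which is still possible from records or contact where consent allows.

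The issue does not extend to bailout subjects, who keep full 5-year follow-up, or to subjects whose procedure never started, who are outside the AT set.

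**Conclusion.** The concern holds and should be fixed. A stated rule ends required follow-up for subjects who remain in the primary analysis, and no passage obliges anyone to learn whether they were alive at day 365.

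The expected effect is small: type I error of at most 0.0395 against 0.0312 at the cited conversion rates, even on the worst assumption about those subjects. The consequence in an individual trial can be decisive, because one death separates success from failure at n = 30. Inflation clearly above 5% requires two or more unfollowed subjects counted alive, or three dropped, at the assumed 60–70% mortality, or one death missed with certainty.

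Confidence is high on the data-collection gap. It is lower on the missing rule for unknown status, since the separate Statistical Analysis Plan was not available. The calculations take all 30 subjects as AT and use the one-sided 0.05 level that reproduces the plan's power.

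**What to change.** - **Sections 7.3, 14.1 and 14.2:** require vital status at day 365 for every AT subject, whatever the valve status and whether or not visits have stopped, by telephone or record check of the kind Section 14.3 describes for missed visits, unless consent to such contact is withdrawn. Who is discontinued need not change.
- **Sections 10.2.9, 11.7 and the glossary cut-off for adverse events:** bring into line with that requirement. Reconcile Section 15.1 with 15.1.1.2 on who is in the primary set.
- **Section 15.1.2:** keep all AT subjects in the primary analysis and state in advance how any status still unknown at day 365 enters the test. Counting unknowns as alive should not be that rule: with two unknowns, even missing at random, it gives P(X ≤ 8 | 28, 0.45) = 0.058.
- **Sensitivity analyses:** report unknown status counted as death, alongside the Kaplan-Meier 1-year estimate with its one-sided 95% upper limit.

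The cost is one contact or record check for a few subjects, plus wording. Counting unknowns as deaths belongs in a sensitivity analysis because of its price as a primary rule: power at 20% mortality, P(X ≤ 8 − u | 30 − u, 0.20), falls from 87% to 79%, 68%, 54% and 11% with u = 1, 2, 3 and 6 unknowns.
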